4.3 Completion of Study

Subjects will be considered to have completed the study if they complete the safety follow-up phone call at Day 12 (± 2).

All reasons for screening failure will be recorded in the electronic case report form (eCRF).

4.4 Discontinuation or Early Termination of Subjects

Subjects who receive SM but withdraw or are withdrawn from participation in the study by the investigator before completion of the study (i.e., after SM administration on Day 1 but prior Day 10), should complete at the earliest time an ET visit. Procedures and assessments listed for Day 10 (see [Table 1](#)) should be completed at the ET visit.

If subject's ET visit occurs ≥ 72 h after the date of subject's last dose, efficacy assessments should not be performed/collected at the ET visit.

The investigator or subjects themselves may stop SM administration at any time for safety or personal reasons. A subject is free to withdraw from the study at any time for any reason without prejudice to their future medical care by the investigator or at the institution. The Sponsor may also withdraw the subject at any time in the interest of the subject's safety. The withdrawal of a subject from the study should be discussed with the Medical Monitor and the investigator before the subject discontinues SM. Subjects removed from the study for any reason will not be replaced.

Reasons for a subject's early discontinuation may include:

- Withdrawal of consent
- Noncompliance of study procedures
- Occurrence of unmanageable AEs
- Lost to follow-up
- Lack of efficacy
- The investigator or the Sponsor believes it is in the best interest of the subject to discontinue the study (i.e., for safety or tolerability reasons)
- Other

If the subject withdraws consent or the investigator discontinues the subjects from the study, the primary reason for the subject's withdrawal, or the investigator's discontinuation

This document is confidential. It contains proprietary information of Supernus Pharmaceuticals, Inc. Any viewing or disclosure of such information that is not authorized in writing by the Sponsor is strictly prohibited. Such information may be used solely for the purpose of reviewing or performing this study.

of the subject should be documented and captured in the eCRF. If a subject is withdrawn for more than one reason, each reason should be documented in the source document and the primary reason should be entered in the eCRF.

If the subject is lost to follow-up, every effort must be made by the study site to contact the subject and to determine the reason for discontinuation/withdrawal. This should include at minimum 3 phone calls, certified letters, email, etc. The measures taken to follow-up must be documented.

Subjects who withdraw will not be replaced.

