The evaluation period includes 4 clinic visits (on days 1, 4, 7 and 10). Subjects will receive SM at the clinic on days 1, 4 and 7. Subjects will not receive SM on days 2, 3, 5, 6, 8, 9 and 10. Subjects will continue their ADT throughout the study. All safety, efficacy, , and pharmacodynamic (PD) assessments and procedures will be performed as outlined in [Table 1](#) and [Table 2](#).

At the end of study (EOS; Day 10) or early termination (ET), if applicable, subjects will return to the clinic for the EOS visit. Approximately 5 days (+2 days) after the last administration of SM (Day 7) and once all study visits are completed; subjects will receive a safety follow-up phone call. Subjects who discontinue the study due to adverse events (AEs) will be followed for at least 30 days following the date of last administration of SM or until resolution, or until, in the medical judgment of the investigator, the event has stabilized or is assessed as chronic.

Duration of Subjects' Participation:

The total study duration for each subject's participation is up to 40 days (screening period [up to 28 days], evaluation period [10 days], and safety follow-up phone call [5 days from Day 7]).

Investigational Medicinal Products, Reference Therapy, Doses and Mode of Administration:

Study Medication: SPN-820 400 mg capsules

Dosage: 2400 mg (six 400-mg capsules) administered once a day every 3 days

Mode of Administration: Oral, as intact capsules, in the morning approximately 3 hours after breakfast

Sampling for [REDACTED] Pharmacodynamic Assessments:

[REDACTED]
[REDACTED]
[REDACTED].

Seven total blood samples will be collected for measurement of BDNF concentrations: 3 pre-dose collections on days 1, 4, and 7; 3 post-dose collections 4 hours after SM administration on days 1, 4, and 7; and 1 collection on Day 10.

Statistical Methodology:

Sample Size: Approximately 50 subjects will be enrolled to achieve approximately 40 subjects completed. This sample size is based on clinical judgment without a power calculation.

Analysis Populations:

The full analysis set (FAS) includes all subjects who receive at least one dose of SM and have a baseline and at least one post-baseline measurement of HAM-D₆.

The safety population includes all subjects who receive at least one dose of SM.

[REDACTED]
[REDACTED].

The PD population includes subjects who receive at least one dose of SM and have a baseline and at least one post-baseline BDNF concentration.

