5.3 Missed Study Medication Administrations or At-Home Phone Calls

Subjects may be discontinued from the study at the discretion of the investigator and in consultation with the Medical Monitor and the Sponsor if:

- 1) the subject misses 1 of the 3 SM administrations, or
- 2) the subject misses >1 of the at-home phone calls.

All discontinuation procedures will be followed as listed on Day 10 of [Table 1](#).

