6 STUDY METHODS

The Schedule of Events and Assessments is provided in [Table 1](#), and a detailed schedule of timed assessments (Window) is provided in [Table 2](#).

All subjects who are enrolled and receive the initial administration of SM on Day 1 will be followed according to the protocol regardless of the number of doses of SM taken, unless consent for follow-up is withdrawn. The Sponsor or Sponsor's designee must be notified of all deviations from the protocol clinic visits or procedures, except as noted, and these procedures, if applicable, will be rescheduled or performed at the nearest possible time to the original schedule. AEs should be reported during clinic visits and during at-home contacts. Subjects will also be instructed to call study personnel to report any AEs during the intervals outside the established study contacts and to come to the clinic/or seek medical care if medical evaluation is needed and as the urgency of the situation indicates. For emergencies and other unscheduled visits to a medical facility other than the clinic, medical records will be obtained by the investigator or qualified designee as source data for study follow-up.

Table 1: Schedule of Events and Assessments

Study Period	Screening	Evaluation Period							Safety/ Follow-Up (FPC ^a)
		Seven-Day Treatment Period						EOS/ ET	
	Clinic	Clinic (Baseline)	Home	Clinic	Home	Clinic	Home	Clinic	Home
Visit Number	1	2	-	3	-	4	-	5	
Study Day	-28 to -1	1	2-3	4	5-6	7	8-9	10	12
Window Visit (days)									+2
Sign informed consent	X								
Review eligibility criteria	X	X							
Demographics	X								
Medical history ^b	X								
Confirm MDD diagnosis	X								
Record prior medications	X								
Confirm stable, therapeutic dose of one study-approved ADT	X								
MINI	X								
Physical examination ^c	X	X						X	
Height	X								
Body weight	X	X		X		X		X	
Calculation of body mass index	X								
Vital signs with orthostatic blood pressure and pulse rate ^d	X	X		X		X		X	
12-Lead ECG ^e	X	X		X		X		X	
Blood sample for hematology	X	X				X		X	
Blood sample for chemistry	X	X				X		X	

This document is confidential. It contains proprietary information of Supernus Pharmaceuticals, Inc. Any viewing or disclosure of such information that is not authorized in writing by the Sponsor is strictly prohibited. Such information may be used solely for the purpose of reviewing or performing this study.

Study Period	Screening	Evaluation Period							Safety/ Follow-Up (FPC ^a)

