4	3	Clinic	Pre-dose		X ^e (-60 min)	X (-60 min)	X (-60 min)	X (-60 min)
			1 hour					
			2 hours		X (±30 min)			
			4 hours		X (±30 min)	X (±30 min)		X (±30 min)
			8 hours		X (±30 min)			
5	–	Home	24 hours		X (±2 h) ^e			
6	–	Home	48 hours		X (±2h) ^f			
7	4	Clinic	Pre-dose		X ^f (-60 min)	X (-60 min)	X (-60 min)	X (-60 min)
			1 hour					
			2 hours		X (±30 min)			
			4 hours		X (±30 min)	X (±30 min)		X (±30 min)
			8 hours		X (±30 min)			
8	–	Home	24 hours		X (±2 h) ^e			
9	–	Home	48 hours		X (±2 h) ^f			
10	5	Clinic	72 hours		X (±2 h) ^g	X (±2 h)	X (±2 h)	X (±60 min)

BDNF = brain-derived neurotrophic factor; CGI-S = Clinical Global Impression – Severity of Illness; h = hours; HAM-D₆ = Hamilton Depression Rating Scale-6 Items;

MADRS = Montgomery–Åsberg Depression Rating Scale; min = minutes; [REDACTED]

a. Time either before (pre-dose) or after SM administration.

b. Administration of the HAM-D₆ and MADRS will be performed preferably by 2 different raters.

c. Seven total blood samples will be collected for measurement of BDNF concentrations: 3 pre-dose collections on days 1, 4 and 7; 3 post-dose collections 4 hours after SM

administration on days 1, 4 and 7; and 1 collection on Day 10.

- e. The HAM-D₆ will be administered remotely on days 2, 5, and 8, approximately 24 hours (± 2 hours) after SM was administered in the clinic on days 1, 4, and 7, respectively.
f. The HAM-D₆ will be administered remotely on days 3, 6, and 9, approximately 48 hours (± 2 hours) after SM was administered in the clinic on days 1, 4, and 7, respectively.
g. The HAM-D₆, MADRS, and CGI-S will be administered on Day 10, approximately 72 hours (± 2 hours) after SM was administered in the clinic on Day 7. The HAM-D₆, MADRS, and CGI-S will be administered prior to any safety assessments.

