6.2 Home Evaluations

On days 2, 3, 5, 6, 8, and 9, subjects will receive a telephone call for safety and efficacy assessments. Subjects will continue to take their ADT.

6.2.1 Days 2, 3, 5, 6, 8 and 9

The following assessments will be conducted remotely by telephone:

- Review AEs
- Review concomitant medications
- Confirm compliance and remind subject to complete the ADT adherence diary
- Administer HAM-D₆ remotely approximately 24 and 48 hours (± 2 hours) after each administration of SM on days 1, 4, and 7 as detailed in [Table 2](#)

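### Protocol 4.4 bars efficacy ratings at an early-termination visit 72 h or more after the last dose, although completers are rated at 72 h ±2 h, so leavers seen at or after that point lose their final HAM-D6, MADRS and CGI-S

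*Protocol*

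**What the plan says.** Section 4.4 of the protocol first says that a dosed subject who withdraws before Day 10 "should complete at the earliest time an ET visit", and that "Procedures and assessments listed for Day 10" should be completed there. That list includes HAM-D6, MADRS and CGI-S. The next paragraph removes the efficacy scales for late attenders: if the "ET visit occurs ≥ 72 h after the date of subject's last dose, efficacy assessments should not be performed/collected" at the visit.

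Four other places bear on this rule:

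- **Synopsis, dosing days:** "Subjects will receive SM at the clinic on days 1, 4 and 7".
- **Table 2, footnote g:** HAM-D6, MADRS and CGI-S "will be administered on Day 10, approximately 72 hours" after the Day 7 dose. The window is ±2 h.
- **Section 5.3:** a subject who misses one of the three doses, or more than one phone call, may be discontinued. "All discontinuation procedures will be followed as listed on Day 10" of Table 1, and no 72 h exception is mentioned.
- **Section 6:** every subject given the Day 1 dose "will be followed according to the protocol regardless of the number of doses of SM taken, unless consent for follow-up is withdrawn".

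SAP 3.9.1 leaves missing efficacy values unimputed and summarises observed cases. SAP 3.10 uses nominal visits. Neither says to which time point a rating taken at an early-termination (ET) visit belongs.

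**The concern.** The cut-off equals the dosing interval, so it falls on the next scheduled clinic visit and inside the window in which completers give their final rating. At the same elapsed time, whether a rating is taken depends on whether the subject is staying or leaving.

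The efficacy results of this single-arm study are observed-case descriptive summaries. A rating that is not taken drops the subject from the 72 h change scores and, read as observed cases, from the response, remission and CGI-S 1-or-2 proportions at that point. The reasons for leaving listed in Section 4.4 include lack of efficacy and unmanageable adverse events, so the omitted subjects may have done worse than those who continued. No later analysis can recover ratings that were never made.

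**Working it through.** **Timing.** Doses are given on Days 1, 4 and 7, and the last rating is on Day 10. Each gap is 3 days × 24 h = 72 h. The completers' window is 72 ± 2 h = 70 to 74 h. The ET bar starts at 72 h, so the overlap is 72 to 74 h, or (74 − 72)/(74 − 70) = half of the completers' window.

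**Clock or calendar.** The rule counts hours from the date of the last dose. By clock time, an ET visit at 71 h may be rated. By calendar date, Day 4 is already three days after Day 1, and any ET visit that day is barred. The protocol does not say which applies.

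**Leaving by a missed dosing visit.** Failure to attend on Day 4 or Day 7 is known only at about 72 h after the previous dose. Any ET visit arranged afterwards is at about 72 h or later. Section 5.3 asks for the Day 10 procedures in these subjects; Section 4.4 refuses the efficacy part.

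**How many.** The plan gives no dropout rate. Section 8.2 gives about 50 enrolled and about 40 completed, so 50 − 40 = 10, and 10/50 = 20%. This is an upper guide on the planning figures: completion requires the Day 12 call (Section 4.3), some leavers have no ET visit, and some are barred separately after a positive drug or alcohol screen (Section 6.5).

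The share of leavers barred depends on ET timing, which the documents do not give. As an illustration, assume that the time of leaving is uniform over the 72 h after the last dose and that the ET visit follows L hours later. Then the share barred = min(1, L/72).

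| Lag L (h, assumed) | Share barred | Of 10 leavers |
|---|---|---|
| 0 | 0% | 0 |
| 12 | 17% | 1.7 |
| 24 | 33% | 3.3 |
| 36 | 50% | 5.0 |
| 48 | 67% | 6.7 |
| 72 or more | 100% | 10 |

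The range is 0% to 100%.

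**What is lost, by scale (Tables 1 and 2).**

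- **HAM-D6:** rated at 2, 4 and 8 h after each dose, and by phone "remotely approximately 24 and 48 hours" after it. Only the point near 72 h is at risk. FAS membership needs one post-baseline HAM-D6, so it is hardly affected.
- **MADRS:** rated pre-dose and at 4 h on dosing days, and on Day 10. A subject who has dose 1, does not attend Visit 3 as scheduled and is barred at ET has only the 4 h value from Day 1. Section 4.1 also mentions MADRS by phone, against Tables 1 and 2 and Section 6.2; this must be reconciled.
- **CGI-S:** rated pre-dose on Days 1, 4 and 7, and on Day 10. The same subject has no post-baseline CGI-S.

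**The case against.** The strongest defence is that the bar is a deliberate exception. Within Section 4.4 it directly follows the Day 10 list, and not rating beyond one dosing interval is a possible choice in a descriptive study without hypotheses. That removes any contradiction inside Section 4.4. It does not explain a cut-off inside the completers' own window, or the absence of an exception in Section 5.3. A wish to keep late ratings out of a summary justifies labelling them, not declining to take them.

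Section 6 also mitigates the problem: subjects who stop study medication but remain in follow-up stay on the schedule and are rated at scheduled visits. The bar then reaches only those who leave the study. This stands.

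A reader might infer two stronger points that the documents do not support:

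- **That most early leavers lose their final ratings.** The ET visit is to take place as early as possible, and before 72 h all three scales are taken. Under the assumption above, a majority requires a lag of more than 36 h, and the documents give no lag.
- **That a subject who attends on Day 4 and stops there goes unrated.** Table 2 schedules all three scales within the 60 minutes before dosing on Days 4 and 7, about 71 to 72 h after the previous dose if doses are given at the same clock time. Such a subject is due those ratings at Visit 3. They are lost only if the visit is treated as an ET visit before any rating is made.

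**Conclusion.** The concern holds for early leavers whose ET visit falls at 72 h or later, including essentially all who leave by missing the Day 4 or Day 7 dosing visit. Their number is unknown, with about 10 of 50 as the upper guide if the planned completion is met. The effect on the primary scale is limited to the roughly 72 h point; the effect on CGI-S, and on MADRS as scheduled in Tables 1 and 2, is larger.

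It is tempting to conclude that the 72 h results are biased in favour of the drug. That direction is plausible, given the listed reasons for leaving, but it is not shown: the bar depends on elapsed time, not on outcome, and the documents do not say who will leave or when. The point is an inexpensive improvement in data collection and a set of sections to reconcile. It does not invalidate the efficacy summaries.

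**What to change.** 1. In Section 4.4, delete the sentence, or set any cut-off beyond the 74 h allowed for completers and state whether it counts from clock time or calendar date.
2. Collect HAM-D6, MADRS and CGI-S at the ET visit and record the hours since the last dose. Keep the separate bar after a positive drug or alcohol screen (Section 6.5).
3. Add one SAP line, as a stated exception to the nominal-visit rule in 3.10: present ET ratings within 72 h ±2 h with the matching 72 h point (Day 4 pre-dose after dose 1, Day 7 pre-dose after dose 2, Day 10 after dose 3), and list later ones separately.
4. Reconcile Sections 4.4, 5.3 and 6 with Table 2, and the phone MADRS in Section 4.1 with Tables 1 and 2 and Section 6.2.

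The cost is small, because subjects already attend the ET visit for the other Day 10 procedures. The downside is that some ratings will be later than 72 h and must be labelled. The change does not supply Day 10 values for subjects who left after dose 1 or 2; it restores only the rating at the point they reached.

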5 STUDY TREATMENT

5.1 Study Medication Identity, Packaging, and Labeling

SM is supplied by the Sponsor as capsules packaged in bottles. Each capsule will contain 400 mg of SPN-820 (Supernus Pharmaceuticals, Inc. product alternative identification number). The capsule is Size 00 elongated (00 EL), white opaque cap and body. Each bottle will contain 40 capsules of 400 mg SPN-820. Each bottle will be labeled with the protocol number.

5.2 Study Medication Administration

SM will be administered orally in the clinic once every 3 days for a 7-day treatment period. SM should be administered in the morning, approximately 3 hours after breakfast.

Subjects will receive a single dose of SPN-820 2400 mg as six 400 mg capsules on days 1, 4, and 7. The capsules will be consumed intact, and splitting the daily dose (e.g., taking part of the daily dose in the morning and the remainder of the daily dose in the evening) is not permitted.

Subjects who cannot tolerate SPN-820 2400 mg should be discontinued from the study at the discretion of the investigator.

Subject will not receive SM on days 2, 3, 5, 6, 8, 9, or 10.

5.3 Missed Study Medication Administrations or At-Home Phone Calls

Subjects may be discontinued from the study at the discretion of the investigator and in consultation with the Medical Monitor and the Sponsor if:

- 1) the subject misses 1 of the 3 SM administrations, or
- 2) the subject misses >1 of the at-home phone calls.

All discontinuation procedures will be followed as listed on Day 10 of [Table 1](#).

5.4 Subjects' Antidepressant Therapy

All subjects must be on stable (for ≥ 6 weeks before screening) therapeutic doses of one of the study-approved ADTs for treatment of their current MDE. The following are the antidepressants approved for the study: citalopram, escitalopram, paroxetine, fluoxetine, sertraline, duloxetine, venlafaxine (immediate release or extended release), desvenlafaxine, vilazodone, levomilnacipran, vortioxetine, bupropion, or dextromethorphan/bupropion (see [Appendix 11.2](#) for study-approved ADTs). If a subject is taking a second ADT or augmentation therapy at screening, the investigator should decide if it is medically appropriate to discontinue the second drug before baseline. If so, the second drug should be discontinued at least 5 half-lives prior to baseline.

Subjects will continue to take their ADT for their current MDE throughout the study and after completion of the study. Subjects will bring their daily supply of ADT at each clinic

visit and continue to take their ADT at home (on days 2,3,5, 6, 8 and 9). Dose adjustments or changes of subjects' ADTs will not be allowed at any time during the study. ADTs approved for use in this study will not be supplied by the Sponsor.

Subjects will receive a paper ADT adherence diary at screening and document the day of each dose of their ADT throughout the study. Subjects must bring their diaries to each clinic visit for review of subject's compliance. This should be reinforced at each clinic visit.

5.5 Method of Assigning Subjects to Treatment

All eligible subjects will receive SPN-820 2400 mg (six 400 mg capsules) on each dosing day.

5.5.1 Blinding

Not applicable.

5.6 Study Medication Handling and Accountability

All SM will be supplied by the Sponsor to the investigator. SM supplies must be stored at 20 to 25°C in an appropriate, secure area (e.g., locked cabinet) and stored according to the conditions specified on the SM label.

Following Sponsor instructions and in compliance with International Council for Harmonisation (ICH) E6 as well as local, state, and federal regulations, the investigator and study staff will be responsible for the accountability of all clinical supplies (receiving, shipment, dispensing, inventory, and record keeping) in a SM accountability log, a copy of which will be collected by the Sponsor at the end of the study.

Under no circumstances will the investigator allow the SM to be used other than as directed by this protocol. SM will not be dispensed to any individual who is not enrolled in the study.

An accurate and timely record of the receipt of all clinical supplies; collection of unused clinical supplies must be maintained with dates. This SM accountability log includes but may not be limited to: 1) documentation of receipt of SM, 2) SM inventory log, and 3) all shipping service receipts. Forms may be provided by the Sponsor. Any comparable forms that the study site wishes to use must be approved by the Sponsor.

The supplies and inventory records must be made available, upon request, for inspection by the designated representative of the Sponsor, or a representative of the Food and Drug Administration (FDA). The assigned Clinical Research Associate (CRA) will review these documents along with all other study conduct documents at specified intervals once SM has been received by the study site. All used, partly used, and unused clinical supplies, including empty containers, are to be returned to the Sponsor at the conclusion of the study, unless a provision is made by the Sponsor for destruction of supplies and containers at the study site. Upon completion of SM accountability and reconciliation procedures by study

site personnel and documentation procedures by Sponsor personnel, SM is to be returned to the Sponsor with a copy of the completed SM disposition form.

